### 7.11.2 Clinical Laboratory Evaluations

Clinical safety laboratory tests include chemistry, hematology, urinalysis, and diagnostic screening. Refer to [Appendix A](#) for scheduled clinical laboratory test measurements and to [Appendix B](#) for the list of all clinical laboratory tests.

Descriptive statistics (N, mean, median, SD, minimum and maximum) of clinical safety laboratory variables will be summarized for baseline, post-dosing, and change from baseline at each visit. Only the scheduled measurements will be included in the summary. No inferential analysis will be performed.

Individual results for hematology and chemistry laboratory tests will be evaluated against the Takeda predefined laboratory markedly abnormal value (MAV) criteria ([Appendix C](#)). All subjects that meet the MAV criteria will be presented in a data listing. If a subject has a MAV for a particular laboratory test, all visits for that subject for that parameter will be listed. The number and percentage of subjects with at least 1 post dose markedly abnormal laboratory test result will be summarized by regimen. The mapping of the subjects with post dose results which meet the MAV criteria will be listed as a table. All post dose clinical lab results within 7 days of the last

dose, including scheduled and unscheduled measurements will be included in the MAV summaries.

All clinical laboratory data will be presented in both SI and conventional units in the data listings. Laboratory data outside of the normal reference range will be flagged on the listing along with values meeting MAV criteria.

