## **10.2.9 Collection and Reporting of AEs, SAEs, Special Interest AEs, and Abnormal LFTs**

### *10.2.9.1 Collection Period*

Collection of AEs (ie, AEs, SAEs, special interest AEs, and abnormal LFTs) will commence at the time the subject signs the informed consent. Routine collection of AEs will continue until the Follow-up Visit 10 to 14 days after the last dose of TAK-906. For subjects who discontinue prior to the administration of trial medication, AEs will be followed until the subject discontinues trial participation.

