### 4.4 Study Design

This is a phase 1, single-sequence, open-label, 2-period crossover trial in approximately 12 healthy male and female (nonchildbearing-potential) subjects. The trial is designed to investigate the effect of a potent CYP3A4 inhibitor (itraconazole) on the PK of TAK-906.

The trial will include a Screening Visit, a Period 1 (Days 1 to 3), followed by a minimum of a 4-day washout from the time of TAK-906 maleate dose, a Period 2 (Days 1 to 6), and a Follow-up Visit.

On Day 1 of Period 1, eligible subjects will be enrolled into the trial and will receive a single PO dose of TAK-906 maleate 25 mg. On Days 1 to 5, inclusive, of Period 2, subjects will receive itraconazole 200 mg once daily (QD) PO solution. Following after an overnight fast of at least 8 hours, a single PO dose of TAK-906 maleate 25 mg will be administered 1 hour after the itraconazole dose on Day 4 of Period 2. Both doses of TAK-906 maleate will be administered after an overnight fast of at least 8 hours as food reduces its bioavailability by approximately 40%.

Itraconazole will be administered to subjects under clinic supervision on an outpatient basis on the morning of Days 1 to 3 of Period 2 and during confinement on Days 4 to 5 of Period 2.

Blood samples for assessment of TAK-906 concentrations will be collected from predose to 48 hours after each dose of TAK-906 maleate. Samples may be assayed for TAK-906 metabolites if deemed necessary. Urine samples will be collected through 48 hours and may be assayed for TAK-906 concentrations and metabolites if deemed necessary for the interpretation of data.

[figure not shown]
Whole blood samples for deoxyribonucleic acid (DNA) pharmacogenomics (PGx) analysis and ribonucleic acid (RNA) isolation will be collected predose on Day 1 of Trial Period 1.

Safety will be assessed by monitoring for adverse events, vital signs, ECGs, clinical laboratory results, and physical examinations throughout each dosing period.

After completion of the trial (or following subject withdrawal), all subjects will return for a Follow-up Visit 10 to 14 days after their last dose of TAK-906 maleate.

A schematic of the study design is shown in [Figure 4.a](#). A schedule of assessments is listed in [Appendix A](#).

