#### 7.11.1 Adverse Events

A treatment-emergent adverse event (TEAE) will be defined as an AE or serious adverse event (SAE) that started or worsened after first study drug administration and within 30 days of last dose of study drug (onset date – date of last dose + 1  $\leq$  30). All AE verbatim terms will be coded by system organ class (SOC) and preferred term (PT) using the MedDRA dictionary.

TEAEs will be summarized by overall and the following categories: Period 1 (onset on and after TAK-906 dosing on Period 1 Day 1 and before the dosing of itraconazole on Period 2 Day 1), Period 2 Day 1 post-dose to Day 4 pre-dose (after itraconazole dosing on Period 2 Day 1 and before TAK-906 dosing on Period 2 Day 4), and Period 2 Day 4 post-dose and thereafter (after TAK-906 and itraconazole dosing on Period 2 Day 4). The tables will include the number and percentage (N [%]) of subjects reporting any event for that term. The following is a list of TEAE summary tables to be generated.

- Overview of TEAEs (at both subject and event level).
- TEAEs by SOC and PT (at both subject and event level).
- Subject Mappings for TEAEs.
- TEAEs by PT.
- Relationship of TEAEs to Study Drug by SOC and PT.
- Drug-Related TEAEs by SOC and PT.
- Intensity of TEAEs by SOC and PT.
- Intensity of Drug-Related TEAEs by SOC and PT.

For each category and overall, subjects reporting more than 1 occurrence for a term (SOC or PT) being summarized will be counted only once using the most extreme incident (most severe for the intensity tables and related for the relationship to study drug tables).

Data listings will be provided for all TEAEs, PTEs, TEAEs that led to study drug discontinuation, TEAEs that led to abnormal liver functions, SAEs, AEs that resulted in death, and AEs occurring more than 30 days after the last dose of study medication.

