### 7.11.3 Vital Signs

Vital sign measurements include body temperature, pulse, respiratory rate, and blood pressure. Refer to [Appendix A](#) for scheduled vital signs measurement visits.

Descriptive statistics (N, mean, median, SD, minimum and maximum) of these vital signs will be summarized by regimen for baseline, post-dosing, and change from baseline at each scheduled time point. For each regimen (period), baseline is defined as the last non-missing vital sign measurement at or prior to predose (time relative to TAK-906 dosing) in the corresponding period. Only the vital signs collected at the scheduled visits or time points will be included in the summary. No inferential analysis will be performed for the observed vital signs.

All individual vital signs that meet Takeda's predefined criteria for markedly abnormal values ([Appendix D](#)) will be listed. The number and percentage of subjects with at least 1 post dose markedly abnormal vital sign measurement will be summarized by regimen. The mapping of the subjects with post dose results which meet the MAV criteria will be listed as a table. All post dose vital signs within 7 days of the last dose, including both scheduled and unscheduled measurements, will be included in the MAV summaries.

All vital sign data will be presented in the listings. Vital sign MAVs will be flagged in the listings.

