### 7.11.4 12-Lead ECGs

The scheduled 12-lead ECG data will be collected according to [Appendix A](#). The ECG parameters include heart rate, PR interval, QRS duration, QT interval, and QT interval with Fredericia's corrections (QTcF).

Quantitative triplicate ECG measurements at each time point will be averaged. Descriptive statistics (N, mean, median, SD, minimum and maximum) of quantitative ECG data will be summarized by regimen for baseline, post-dosing, and change from baseline at each scheduled time point. For each regimen (period), baseline is defined as the last non-missing ECG measurement at or prior to predose (time relative to TAK-906 dosing) in the corresponding period. Only the ECGs collected at the scheduled visits or time points will be included in the summary. No inferential analysis will be performed for the observed ECGs.

For ECG interpretation data, shift table will be provided as the number of subjects to assess interpretation status change from baseline to each scheduled post-baseline measurement by regimen. In the ECG shift table, the best value out of triplicate ECG interpretations will be used to represent baseline evaluation, and the worst value will be used to represent post baseline evaluation.

All individual ECGs that meet Takeda's predefined criteria for markedly abnormal values (Appendix E) will be listed. The number and percentage of subjects with at least 1 markedly abnormal ECG measurement will be summarized by regimen. The mapping of the subjects who meet the MAV criteria will be listed as a table. All post dose ECGs within 7 days of the last dose, including both scheduled and unscheduled measurements, will be included in the MAV summaries.

All ECG data will be presented in the listings. ECG MAVs will be flagged in the listings.

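### The markedly abnormal value tables stop 7 days after the last dose and so leave out every completer's Follow-up labs, vital signs and ECGs

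*SAP*

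**What the plan says.** The SAP sets the same limit for three kinds of MAV summary:

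- Laboratory (SAP 7.11.2): "All post dose clinical lab results within 7 days of the last" dose.
- Vital signs (SAP 7.11.3): "All post dose vital signs within 7 days of the last dose, including both scheduled and unscheduled measurements".
- ECGs (SAP 7.11.4): "All post dose ECGs within 7 days of the last dose, including both scheduled and unscheduled measurements".

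These summaries count, by regimen, the subjects with at least one MAV. None of the three sections says whether the last dose means TAK-906 or itraconazole, and none gives a reason for 7 days. Protocol 11.1.4.2 to 11.1.4.4 contain no such limit.

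On timing, SAP 4.4 states that "all subjects will return for a Follow-up Visit 10 to 14 days after their last dose of TAK-906 maleate". The schedule in SAP Appendix A puts hematology, chemistry, vital signs and ECG at that visit.

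Adverse events follow other windows. SAP 7.11.1 counts an event as treatment-emergent if it starts or worsens after first dosing and "within 30 days of last dose of study drug". Protocol 10.2.9.1 says: "Routine collection of AEs will continue until the Follow-up Visit 10 to 14 days after the last dose of TAK-906".

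**The concern.** A table counting subjects with at least one post-dose abnormality is normally read as covering every scheduled post-dose assessment. Here the last scheduled assessment cannot enter it for anyone who completes the trial. A liver test or QTcF value that first meets the MAV criteria at Follow-up would not be counted, while an adverse event starting on the same day would be counted as treatment-emergent. Safety and tolerability is the only secondary objective, and the MAV tables are the planned displays that count subjects against preset thresholds.

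**Working it through.** The plan states no figure to reproduce, so the check is date arithmetic.

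**Inputs**
- Last TAK-906 dose: Period 2 Day 4 (SAP 4.4).
- Last itraconazole dose: Period 2 Day 5 (SAP 4.4).
- Follow-up: 10 to 14 days after the last TAK-906 dose (SAP 4.4).
- MAV limit: 7 days after the last dose (SAP 7.11.2 to 7.11.4).
- Minimum washout: 4 days from the Period 1 TAK-906 dose (SAP 4.4).
- TEAE rule: onset date minus last dose date plus 1 is at most 30 (SAP 7.11.1).

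**Completers**
- Follow-up day = 4 + 10 to 4 + 14 = Period 2 Days 14 to 18.
- Days after the last itraconazole dose = 14 − 5 to 18 − 5 = 9 to 13.
- Days after the last TAK-906 dose = 10 to 14.
- Both ranges lie wholly above 7. Inclusive counting only adds a day.
- The last scheduled assessment inside the limit is Day 6, which is 6 − 5 = 1 day after itraconazole and 6 − 4 = 2 days after TAK-906.

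**What is left out after the combination**
- Hematology and chemistry are scheduled on Day 6 and at Follow-up, so 1 of 2 panels is omitted.
- ECGs have post-dose times of 1, 2, 4, 8 and 48 hours (footnote c) plus Follow-up, so 1 of 6 time points is omitted. Footnote d gives the same times for heart rate and blood pressure.
- The schedule table is broken in the text available. The ECG and vital-sign marks at Follow-up are inferred: 48 hours after a Day 4 dose is Day 6, which leaves the last mark for Follow-up.

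As an illustration, one subject among 12 with a first MAV at Follow-up would appear as 0/12 instead of 1/12 (8.3%).

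**Early withdrawals**

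Suppose a subject stops after itraconazole on Period 2 Day d, with d = 1, 2 or 3, after the minimum washout. The last itraconazole dose is then 4 + d − 1 days after the Period 1 TAK-906 dose, and Follow-up is 10 to 14 days after that TAK-906 dose.

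| Last itraconazole dose | Days after TAK-906 | Follow-up, days after last itraconazole dose |
|---|---|---|
| Day 1 | 4 | 6 to 10 |
| Day 2 | 5 | 5 to 9 |
| Day 3 | 6 | 4 to 8 |

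These can fall inside 7 days, and a longer washout brings Follow-up closer still. If the last dose means TAK-906, Follow-up is 10 to 14 days away for these subjects too. The undefined term therefore matters for them, though not for completers.

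**TEAE window**
- The rule admits onsets 0 to 29 days after the last dose, which is 30 calendar days.
- Counted the same way, Follow-up is day 9 + 1 = 10 to 13 + 1 = 14 from the last itraconazole dose. Routine collection covers about 10 to 14 of the 30 days (33% to 47%) and leaves 16 to 20 (53% to 67%).
- An event starting on the day of Follow-up gives 10 to 14, below 30, so it counts as treatment-emergent.

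**The case against.** The strongest reply is that the limit is a reasonable choice and hides nothing. It applies only to the MAV summaries. SAP 7.11.2 lists every visit for a subject and parameter with a MAV, flags MAVs in the listings, and gives descriptive statistics, with minimum and maximum, at each visit. SAP 7.11.3 and 7.11.4 list all MAVs, and the ECG interpretation shift table covers each scheduled post-baseline measurement. Under Protocol 10.2.9.4, ALT or AST above 3 times the upper limit on two consecutive occasions is recorded as an adverse event. With about 12 subjects, a flagged listing is easy to read. MAV counts are also given by regimen, and Protocol 4.1 puts the TAK-906 half-life at about 4 hours, so 7 days is 168/4 = 42 half-lives. Counting later values under the combination could attribute to it values seen after dosing ended.

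Most of this stands. A reader might infer that Follow-up results go unreported; the documents do not support that. The attribution argument is a good reason not to put Follow-up values in a regimen column. It is not a reason to leave them out of the table, because a separate column meets it.

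A reader might also infer that the 30-day TEAE window is not collected and should end at Follow-up. That goes too far. Adverse events are collected routinely up to Follow-up. After that, Protocol 10.2.9.3 still asks for spontaneously reported serious events considered related to trial participation. The 30 days are an upper bound for classification, the same in Protocol 11.1.4.1 and SAP 7.11.1, and no completer's routinely collected post-dose event is lost to it. Ending it at Follow-up would drop later related serious events from the TEAE tables. MAV and TEAE windows may also differ, since they serve different purposes.

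**Conclusion.** The point holds in a limited form. For every completer, the 7-day rule keeps all scheduled Follow-up labs, vital signs and ECGs out of the MAV counts, whichever drug the last dose refers to. After the combination that is 1 of 2 lab panels and, from the footnoted times, 1 of 6 ECG time points. The result rests on dosing as scheduled and on reading the broken schedule table as described. It does not extend to every subject, because some who withdraw on Period 2 Days 1 to 3 may have Follow-up inside the limit.

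The consequence is an incomplete count in descriptive tables, not lost data or a biased test. The 1/12 figure is illustrative; the documents give no expected MAV rate. The mismatch between the TEAE window and routine collection is a matter of labelling and no reason to change the rule.

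**What to change.** In SAP 7.11.2, 7.11.3 and 7.11.4, let the MAV summaries run through the Follow-up Visit. Show Follow-up as a separate column beside the regimen columns, so that values taken after dosing ended are not attributed to a regimen. State whether the last dose means TAK-906, itraconazole, or the later of the two.

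Leave the 30-day window in SAP 7.11.1 and Protocol 11.1.4.1 as it is. At most, add a footnote to the TEAE tables that routine collection ends at the Follow-up Visit and that only spontaneously reported, related serious events are expected afterwards.

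The cost is SAP wording and one more column in the MAV tables. All the data are already scheduled for collection. The small downside is that the added column holds values taken after dosing ended, which its label should make plain.

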### 7.11.3 Vital Signs

Vital sign measurements include body temperature, pulse, respiratory rate, and blood pressure. Refer to [Appendix A](#) for scheduled vital signs measurement visits.

Descriptive statistics (N, mean, median, SD, minimum and maximum) of these vital signs will be summarized by regimen for baseline, post-dosing, and change from baseline at each scheduled time point. For each regimen (period), baseline is defined as the last non-missing vital sign measurement at or prior to predose (time relative to TAK-906 dosing) in the corresponding period. Only the vital signs collected at the scheduled visits or time points will be included in the summary. No inferential analysis will be performed for the observed vital signs.

All individual vital signs that meet Takeda's predefined criteria for markedly abnormal values ([Appendix D](#)) will be listed. The number and percentage of subjects with at least 1 post dose markedly abnormal vital sign measurement will be summarized by regimen. The mapping of the subjects with post dose results which meet the MAV criteria will be listed as a table. All post dose vital signs within 7 days of the last dose, including both scheduled and unscheduled measurements, will be included in the MAV summaries.

All vital sign data will be presented in the listings. Vital sign MAVs will be flagged in the listings.

### 7.11.4 12-Lead ECGs

The scheduled 12-lead ECG data will be collected according to [Appendix A](#). The ECG parameters include heart rate, PR interval, QRS duration, QT interval, and QT interval with Fredericia's corrections (QTcF).

Quantitative triplicate ECG measurements at each time point will be averaged. Descriptive statistics (N, mean, median, SD, minimum and maximum) of quantitative ECG data will be summarized by regimen for baseline, post-dosing, and change from baseline at each scheduled time point. For each regimen (period), baseline is defined as the last non-missing ECG measurement at or prior to predose (time relative to TAK-906 dosing) in the corresponding period. Only the ECGs collected at the scheduled visits or time points will be included in the summary. No inferential analysis will be performed for the observed ECGs.

For ECG interpretation data, shift table will be provided as the number of subjects to assess interpretation status change from baseline to each scheduled post-baseline measurement by regimen. In the ECG shift table, the best value out of triplicate ECG interpretations will be used to represent baseline evaluation, and the worst value will be used to represent post baseline evaluation.

All individual ECGs that meet Takeda's predefined criteria for markedly abnormal values (Appendix E) will be listed. The number and percentage of subjects with at least 1 markedly abnormal ECG measurement will be summarized by regimen. The mapping of the subjects who meet the MAV criteria will be listed as a table. All post dose ECGs within 7 days of the last dose, including both scheduled and unscheduled measurements, will be included in the MAV summaries.

All ECG data will be presented in the listings. ECG MAVs will be flagged in the listings.

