### **9.1.10 12-Lead ECG**

Special care must be taken for proper lead placement by qualified personnel. Skin should be clean and dry before lead placement. Subjects may need to be shaved to ensure proper lead placement. Female subjects may need to remove their bras.

Subjects should be resting in a semirecumbent position for at least 5 minutes before each ECG measurement.

QT intervals with Fridericia correction method (QTcF) will be used to calculate QT intervals in this trial.

Before each trial period, a predose ECG will be obtained within approximately 30 minutes before dosing. This measurement will be used as the Baseline. The principal investigator should arrange to have a trial cardiologist available as needed to review ECG tracings with abnormalities.

If a subject demonstrates an increase in QTcF interval  $\geq 40$  msec compared with a predose baseline measurement, the ECG will be repeated within 5 minutes. The average value of the QTcF interval from the 2 ECGs will represent the value at that time point. If the average QTcF interval increase from Baseline for any postdose time point is  $\geq 40$  msec, the subject will continue to be monitored by repeat 12-lead ECGs every 60 minutes for at least 4 hours or until the QTcF is within 40 msec of the baseline value. If prolongation of the QTcF interval  $\geq 40$  msec persists, a consultation with a trial cardiologist may be appropriate and the sponsor should be notified.

If the QTcF interval is  $\geq 500$  msec, the sponsor should be notified and the ECGs should be reviewed by a cardiologist. The subject should be telemetry-monitored (until the QTcF is  $<500$  msec) or should be considered for transfer to a location where closer monitoring is available.

If the subject has unstable hemodynamics, or has any clinically significant dysrhythmias noted on telemetry, the subject should be immediately transferred to an acute care setting for definitive therapy.

If repeat ECGs are required, the clinical site will decide whether to leave the electrodes in place or mark the position of the electrodes for subsequent ECGs. To mark the position of the electrodes, 12-lead electrode sites will be marked on the skin of each subject with an ECG skin marker pen to ensure reproducible electrode placement.

The following ECG parameters will be recorded: HR, PR-interval, QRS-duration, QT-interval, QTcF-interval, and the interpretation of the ECG profile by the principal investigator.

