#### **11.1.4 Safety Analysis**

The safety set will be used for all summaries of safety parameters. These summaries will be presented by regimen (TAK-906 maleate alone, itraconazole alone, and TAK-906 maleate with itraconazole).

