##### *11.1.4.4 ECGs*

Baseline, postdose, and changes from Baseline in quantitative ECG parameters will be summarized by regimen. Shift tables for each will be generated to show the investigator's ECG interpretations at each postdose collection by the interpretation at Baseline.

All ECG data will be provided in the data listings.

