#### 7.1.1 Definition of Study Days and Baseline

Study Day 1 is defined as the date of the first dose of study drug, as recorded on the electronic case report form (eCRF) study drug administration page. Other study days are defined relative to Study Day 1, with Day 1 being Study Day 1 and Day -1 being the day prior to Study Day 1. Study days prior to the first dose of study drug will be calculated as: [date of assessment/event – date of first dose of study drug]. Study days on or after the first dose of study drug will be calculated as: [date of assessment/event – date of first dose of study drug + 1].

Unless specified otherwise, baseline is defined as the last non-missing measurement prior to the first dose of study drug.

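### The protocol asks for ECG change under itraconazole alone, but the only ECG scheduled in that state is used solely as the Period 2 baseline, so the change is never tabulated

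*SAP*

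**What the plan says.** **Regimens.** Protocol 11.1.4 says of the safety parameters: "These summaries will be presented by regimen (TAK-906 maleate alone, itraconazole alone, and TAK-906 maleate with itraconazole"). Protocol 11.1.4.4 then states: "Baseline, postdose, and changes from Baseline in quantitative ECG parameters will be summarized by regimen".

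**ECG baseline in the SAP.** SAP 7.11.4 says: "For each regimen (period), baseline is defined as the last non-missing ECG measurement at or prior to predose (time relative to TAK-906 dosing"). Each period thus has its own reference value. This replaces the general rule in SAP 7.1.1: "Unless specified otherwise, baseline is defined as the last non-missing measurement prior to the first dose of study drug".

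**ECG baseline in the protocol.** Protocol 9.1.10 says: "Before each trial period, a predose ECG will be obtained within approximately 30 minutes before dosing", and adds: "This measurement will be used as the Baseline".

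**Timing.** Footnote (c) of the schedule, in both documents, times the ECGs at 0, 1, 2, 4, 8 and 48 hours relative to TAK-906. Itraconazole is given on Period 2 Days 1 to 5, and 1 hour before TAK-906 on Day 4 (Protocol 9.4).

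**Other safety data.** For adverse events, SAP 7.11.1 does define an itraconazole-alone window: "Period 2 Day 1 post-dose to Day 4 pre-dose (after itraconazole dosing on Period 2 Day 1"). That window closes at the Day 4 TAK-906 dose. Laboratory values "will be summarized for baseline, post-dosing, and change from baseline at each visit", with no baseline of their own, so the 7.1.1 default applies to them.

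**The concern.** The protocol names itraconazole alone as a regimen for the safety summaries. The SAP carries it through for adverse events but not for ECGs. The one ECG that could describe that regimen is used only as the value subtracted from later Period 2 readings.

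Two things are then missing from the tables: the change under itraconazole alone, and the distance of the combination from drug-free values. The secondary objective is the safety of TAK-906 with and without the inhibitor. The planned changes show what TAK-906 adds in each state. They do not show whether the Period 2 starting point had already moved.

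**Working it through.** The documents state no figure to reproduce. The check sets the passages side by side, followed by simple algebra.

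**1. Count the regimens.** Protocol 11.1.4 has three. SAP 7.11.4 treats regimen as period, and there are two periods, so it has two. The only explicit regimen list in the SAP (7.9.1, for PK) also has two entries.

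**2. Count the itraconazole doses before the Period 2 ECG baseline.** Days 1 to 3 give 3. If the predose ECG falls in the hour between the two Day 4 doses, the count is 4. If 9.1.10's window of about 30 minutes refers to TAK-906, 4 is the normal case.

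**3. Count the usable ECGs.** In both schedules the ECG row shows no mark on Period 2 Days 1 to 3, as far as the extracted table can be read. That leaves no visible Period 2 ECG before itraconazole, and one under itraconazole alone (Day 4 predose).

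**4. What the baseline removes.** Let B1 be the Period 1 Day 1 predose value, B2 the Period 2 Day 4 predose value, and Y a Period 2 postdose value. Then

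Y − B1 = (Y − B2) + (B2 − B1).

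The SAP tabulates Y − B2, which is TAK-906's added effect. B2 − B1 is the itraconazole-alone change plus any period drift. Neither B2 − B1 nor Y − B1 is tabulated.

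- Shift table: if all three Day 4 predose tracings are already abnormal, the baseline counts as abnormal and a later abnormal reading shows no shift.
- Appendix E QTcF change criterion (at least 30 ms change and at least 450 ms): if itraconazole has moved a subject by d ms before Day 4 predose, the change part is met only at a total of 30 + d ms from drug-free. For an assumed d = 10 that is 40 ms.

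**5. Spacing.** Period 2 Day 1 is at least 4 days after Period 1 Day 1, and Day 4 is 3 days later: 4 + 3 = at least 7 days between B1 and B2.

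**6. Illustration of the flag.** The documents give neither an itraconazole QTcF effect (d) nor a TAK-906 effect (t), so every input here is assumed. The simulation used 1,000,000 subjects per scenario: subject means normal with SD 15 ms, one predose value per period, five postdose values, flag if at least 500 ms or if the change criterion is met. With population mean 410 ms and within-subject SD 8 ms, the expected number flagged out of 12 is:

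| d (ms) | t (ms) | Baseline B1 | Baseline B2 |
|---|---|---|---|
| 5 | 0 | 0.07 | 0.03 |
| 5 | 5 | 0.26 | 0.12 |
| 5 | 10 | 0.75 | 0.40 |
| 10 | 0 | 0.26 | 0.05 |
| 10 | 5 | 0.74 | 0.18 |
| 10 | 10 | 1.69 | 0.58 |

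With d = 0 the two baselines give the same expected count. With t = 0, mean 410 or less, d up to 10 and within-subject SD 5 to 10, the difference stays below 0.4 of a subject; the largest is 0.60 against 0.21. A 5 ms period drift with d = 0 gives the same counts as d = 5, so the flag cannot separate the two.

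**The case against.** **The SAP baseline follows the protocol.** A reader might infer that the SAP departed from the protocol or chose a wrong baseline. The documents do not support that. Protocol 9.1.10 sets a baseline for each period and footnote (c) ties ECG times to TAK-906. A predose reference within the period is also the right one for TAK-906's added effect. This stands: the protocol asks for a regimen in 11.1.4 that its own ECG schedule barely covers, and the SAP inherits the mismatch.

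**Nothing is lost from the record.** All ECG data are listed, so with about 12 subjects each paired difference and its SD can be computed. Both period baselines are also summarised, and where the same subjects contribute, the difference of the two means is the mean change. This stands too. What is missing is a required summary, not the data.

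**A cross-period difference is not the protocol's Baseline.** Protocol 9.1.10 defines Baseline by period, so Day 4 predose minus Period 1 predose is a workaround and covers one time point only. That is fair. It is, however, the nearest available answer to 11.1.4, and its reference value fits the SAP 7.1.1 default. The combination's change from drug-free values goes beyond what any section requires; it is useful for the secondary objective but not mandated.

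**The different laboratory baseline is no defect in itself.** Agreed. Serial, dose-timed ECGs can reasonably have their own baseline.

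**A reader might infer that a QTcF safety signal will be hidden.** The documents do not support that either. They give no value for an itraconazole or TAK-906 effect, the absolute limits do not depend on baseline, and large differences in flag counts need large assumed effects.

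**Conclusion.** The point holds as a minor, descriptive, secondary-safety gap. Following the SAP as written, the itraconazole-alone ECG change called for by Protocol 11.1.4 and 11.1.4.4 is not produced, and no reason for dropping it is given. Any itraconazole shift present by Day 4 predose is absent from the Period 2 ECG change summaries, the shift table and the change part of the QTcF criterion. That structural gap does not depend on the size of the shift; its practical importance does, and the documents do not give that size. The flag counts are illustrative only.

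The conclusion assumes that no ECG is scheduled on Period 2 Days 1 to 3. The extracted table is broken, so this is the visible reading and not a certainty. Listings, absolute ECG limits and the primary PK comparison are unaffected.

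One wording conflict needs settling in any case. Protocol 9.1.10 places the baseline ECG before each trial period, and Period 2 dosing starts with itraconazole on Day 1, whereas footnote (c) and SAP 7.11.4 tie it to TAK-906 on Day 4.

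**What to change.** Keep the period-specific change in SAP 7.11.4 as the measure of TAK-906's added effect, and add:

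1. a descriptive summary of Day 4 predose minus Period 1 Day 1 predose, labelled as the itraconazole-alone ECG change;
2. for Period 2, the change from the Period 1 Day 1 predose value beside the existing change.

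Footnote both as confounded with period and based on readings at least 7 days apart. Reconcile the baseline wording in Protocol 9.1.10 with footnote (c) and SAP 7.11.4. If that shows a Period 2 ECG taken before itraconazole, it would be the closer reference, 3 days before Day 4.

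Optional: evaluate the Appendix E QTcF change criterion against the Period 1 predose value as well, labelling the baseline used for each flag, and add the same change for vital signs. Vital signs matter less here because Appendix D has absolute limits only. If the sponsor prefers not to add the itraconazole-alone summary, the SAP should say so and give the reason.

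The cost is SAP wording and a few table rows or columns, from ECGs already scheduled. The drawback is a noisier comparison that, in a single-sequence design without a control, cannot separate itraconazole from period drift. It supplements the existing change and does not replace it.
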